7.6 Analysis of Tapering Strategies

Among the subset of participants on high-dose opioid therapy at baseline we will modify the analyses discussed above by adding the tapering assignment as an explanatory measure to the

model structure in the same manner as the TCM/IPT measure is included in the models. We will use comparable testing and estimation approaches to assess whether the expanded tapering option results in better outcomes in this subpopulation.

7.7 Analysis of Adverse Events

Information about hospitalizations, ED visits, SUD admissions, and other adverse events will be extracted from VA administrative data. We will compare intervention arms with respect to the 1) proportion of individuals reporting any hospitalization, ED visit, and SUD admission and 2) number of hospitalization, ED visit, or SUD admissions per person at a) each assessment time-point and b) overall using, respectively, Pearson chi-square tests and, given the reasonable large sample in each arm, large sample normal approximation based z-tests. Similar comparisons will be made between other adverse events. We will also break these comparisons out by baseline dosage and assignment to the expanded taper options arm.

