4.3.3 Eligibility pre-screening

Potentially eligible patients will be identified through pre-screening searches of VA datasets. This pre-screening will be done centrally by data team members at the coordinating center, creating monthly lists of potentially eligible patients by site.

Pharmacy dispensing data will be used to identify patients on long-term moderate-to-high dose opioid therapy, defined for prescreening purposes as meeting the following criteria:

- ≥ 84 days' supply of qualifying opioid analgesic dispensed within the 90 days prior to the date of eligibility assessment; and
- Opioid daily dose ≥ 20 ME mg in the prior 90 days

To avoid recruiting patients with dementia, unstable psychiatric disorder, or those being treated for pain due to active cancer or terminal disease or for opioid use disorder, patients will not be selected if they have any of the following:

- Any chemotherapy, radiation oncology, hospice care, dementia clinic, adult day clinic, current nursing home residence, or opioid treatment program visit in the year prior to the study period
- Any diagnosis of dementia
- Active CPRS flag indicating high risk for suicide

- Limited life expectancy health factor at any visit in the past 12 months

To maintain a steady enrollment rate, only a selection of potentially eligible patients from permitting PCPs at active study sites will be contacted each month by the coordinating center for centralized recruitment. Selected preliminarily eligible patients will be given a study ID number and their names, addresses, and telephone numbers will be loaded into the study tracking application.

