6.3 Administrative Data

6.3.1 Data sources

National VA datasets and the environment for analyzing them are provided by VA Informatics and Computing Infrastructure (VINCI). A VINCI project workspace will be used to access data, construct covariates, and perform primary and secondary analyses.

We will use administrative data to determine eligibility, covariates and outcomes, including the following:

- Patient eligibility criteria from outpatient pharmacy and inpatient and outpatient data domains
- Relationships of patients and primary care providers from PCMM domain
- Patient demographics from patient data domain
- Patients distance and drive time from VA facilities from geographic access data sets created by the planning services and support group
- Physical and mental health diagnoses from inpatient and outpatient data domains
- Prescriptions and drug dispensing from outpatient pharmacy domain
- Pain treatment variables from outpatient and lab chemistry data; outpatient pharmacy data; and outpatient, procedure code, and fee basis data domains
- Hospitalizations, ED visits, and SUD treatment admissions from inpatient, outpatient, procedure code, and fee basis data domains
- COVID-19 test results

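### Section 7.7 tests hospitalizations and ED visits without adjusting for each patient's prior-year events; the tests are valid, but a cheap gain in precision is left unused

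*Combined protocol and SAP*

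**What the plan says.** Section 7.7 defines two safety summaries: the "proportion of individuals reporting any hospitalization, ED visit, and SUD admission" and the "number of hospitalization, ED visit, or SUD admissions per person". Each is compared between arms at every assessment point and overall, "using, respectively, Pearson chi-square tests and, given the reasonable large sample in each arm, large sample normal approximation based z-tests". No covariate is named. Baseline information enters only through stratified tables: "We will also break these comparisons out by baseline dosage and assignment to the expanded taper options arm".

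Section 6.3.1 lists "Hospitalizations, ED visits, and SUD treatment admissions from inpatient, outpatient, procedure code, and fee basis data domains" among the administrative data, and opens its list with "We will use administrative data to determine eligibility, covariates and outcomes". Section 4.3.3 already looks back a year in VA data for other contacts, for example an "opioid treatment program visit in the year prior to the study period".

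By contrast, the linear models in 7.4 (change in BPI) and 7.5 (continuous secondary outcomes) include the baseline value of the outcome, and 7.3 and 7.5 ask for point and interval estimates. Section 7.7 asks only for tests.

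**The concern.** Use of hospital and emergency care differs widely between patients, and some of that difference may persist from one year to the next. A raw two-group test leaves all of it in the error term. If the patient's own prior-year count predicts the follow-up count, conditioning on it removes part of the noise at no cost in validity.

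The direction of the loss matters because these are harm outcomes. A less precise comparison makes a real increase in one arm more likely to be reported as no difference, in a population that 10.4.2 expects to carry a heavy burden of comorbidity.

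**Working it through.** **Inputs from the documents.** 970 enrolled and at least 776 assessed at 12 months (7.1); equal allocation (4.3.9), so 485 and 388 per arm; 50% v 60% response at a 0.05 two-sided level (7.1.1); 35% on high dose (7.1.1). For 7.7 the documents give no event rate, significance level, target difference or power. Two-sided 0.05 is carried over. Event rates, rate ratios and the correlation ρ between prior-year and follow-up events are assumptions. As events come from administrative data, 485 per arm is used.

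**1. The plan's nearest stated figure: chi-square power for the primary outcome.** With 388 per arm, the null SE is √(2 × 0.55 × 0.45 / 388) = 0.03572 and the alternative SE is √((0.25 + 0.24) / 388) = 0.03554. Then (0.10 − 1.96 × 0.03572) / 0.03554 = 0.844, giving power 80.1%. The stated 80% reproduces.

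**2. What the raw chi-square can detect in 7.7.** At 485 per arm, 80% power needs an absolute increase of about 4.7 points from 5%, 6.1 from 10%, 7.7 from 20% or 8.6 from 30% (control rates assumed).

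**3. Analytic effect of adjustment.** The variance of the arm difference is multiplied by about 1 − ρ². A test with 80% raw power has non-centrality 1.960 + 0.842 = 2.802. Adjusted power is Φ(2.802 / √(1 − ρ²) − 1.960), and the equivalent sample size is 970 / (1 − ρ²).

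| ρ | 1 − ρ² | Power, from 80% | Equivalent N |
|---|---|---|---|
| 0.2 | 0.96 | 81.6% | 1,010 |
| 0.3 | 0.91 | 83.6% | 1,066 |
| 0.4 | 0.84 | 86.4% | 1,155 |
| 0.5 | 0.75 | 89.9% | 1,293 |
| 0.6 | 0.64 | 93.8% | 1,516 |

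**4. Simulation.** 970 patients 1:1, gamma-distributed patient rates correlated between years, Poisson counts, 1,500 replicates. The planned tests are set against linear regression on arm, prior-year count and any prior event, with robust SE. Randomisation strata were not simulated.

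| Assumed setting | ρ | Counts: raw → adjusted | Any event: raw → adjusted |
|---|---|---|---|
| Control any-event 23%, rate ratio 1.5 | 0.17 | 85.9 → 87.5% | 67.4 → 69.1% |
| | 0.31 | 85.5 → 88.8% | 67.1 → 71.5% |
| | 0.41 | 84.4 → 91.5% | 66.7 → 71.1% |
| Control any-event 40%, rate ratio 1.35 | 0.25 | 80.7 → 82.3% | 49.2 → 50.9% |
| | 0.43 | 80.1 → 88.3% | 49.4 → 53.8% |
| | 0.57 | 80.0 → 93.7% | 50.1 → 59.3% |
| Rare (about 4%, SUD-like), rate ratio 2 | 0.09 | 63.4 → 64.2% | 55.9 → 55.4% |
| | 0.17 | 62.6 → 63.3% | 54.3 → 55.9% |
| | 0.25 | 62.7 → 67.3% | 56.3 → 58.1% |
| No effect | 0.31 | 4.3 → 4.5% | 4.3 → 5.0% |

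The last row is type I error.

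**5. Hospitalization-like counts, mean 0.5 a year, 40% increase, 485 per arm (400 replicates).** 78 → 80% at ρ = 0.2, 78 → 84% at 0.3 and 82 → 89% at 0.5. The Monte Carlo SE of each power is about √(0.8 × 0.2 / 400) = 2 points. ED-like counts (mean 1.2, 25% increase, ρ about 0.55) went from 75% to 89%.

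**6. Choice of model.** In the ρ = 0.5 hospitalization setting, a negative binomial model with the raw prior count as covariate reached 86% in the run where the z-test had 82% and the linear model 89%. In a 500-replicate run it reached 82% where the z-test had 76% and the linear model 88%. It recovers only about half the gain.

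**7. Smaller comparisons.** High-dose patients number about 970 × 0.35 = 340, or 170 per group; with 80% retention, about 135. At ρ = 0.5 with a 40% increase (2,000 replicates), power goes from 38% to 47% at 170 and from 29% to 38% at 135. Adjustment helps, but does not make these break-outs well powered.

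**The case against.** The strongest reply is that nothing here is an error. The planned tests hold their level, no passage is contradicted and no stated figure fails. That stands.

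The second reply is that the key input is missing: the documents do not report how well prior-year events predict follow-up events. Several features could weaken the link. Sections 4.2 and 4.3.3 remove unstable psychiatric disease, end-stage illness, chemotherapy, hospice and nursing-home patients and those flagged for suicide risk. COVID-19 items appear in the assessment schedule (6.2.3), so prior and follow-up years may fall in different periods of care use. This also stands, and it is why the gain is given as a range starting near 2 points.

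Third, unadjusted analysis is not peculiar to 7.7: the initial primary model in 7.3 has no baseline covariate either, although its outcome is defined relative to baseline. The contrast with 7.4 and 7.5 shows that the plan accepts baseline adjustment, not that 7.7 breaks a rule.

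A reader might also infer that these are the trial's main harm comparisons. The documents do not rank them so. Adverse effects are also patient-reported at every assessment (6.2.3), 7.5 analyses physical symptoms with baseline adjustment, and serious events are tracked and reviewed separately (10.2, 10.3, 10.5).

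What survives is narrow: the covariate appears to be within reach, a weak one costs almost nothing at this sample size, and a strong one buys useful precision.

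**Conclusion.** The point holds as a cheap precision gain, at low to moderate priority. The loss is precision, not bias or inflated error.

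On assumed rates at 485 per arm, the gain for hospitalization and ED-visit counts is roughly 2 to 3 points of power at correlation 0.2, about 3 to 6 at 0.3, and about 7 to 14 at 0.5 to 0.55. For any-event proportions it is about 2 to 8 points, with 9 in the single most favourable run. For rare SUD admissions it is essentially nil; the one larger gain, about 5 points on counts, needed fully stable patient propensity.

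Two stronger readings are tempting. One is that the planned safety tests are unsound; they are valid. The other is that they will miss real harms to a known and large extent. The documents fix neither the event rates nor the correlation, and the largest gains come from assuming that each patient's propensity is unchanged between years, which is the favourable case.

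That prior-year counts can be extracted is itself an inference, from the data sources in 6.3.1 and the one-year look-back in 4.3.3. The plan does not say that it will be done.

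**What to change.** In 7.7, before event data are examined by arm:

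- For the overall 12-month hospitalization and ED-visit counts, pre-specify a linear regression with robust standard errors on assigned arm, the patient's count of the same event in the 12 months before baseline, and the randomisation strata (site and dose category). Report the adjusted mean difference with 95% CI.
- For any hospitalization and any ED visit, report a covariate-standardised risk difference with 95% CI, using any prior-year event as covariate, so that the estimate remains a marginal one.
- Keep the raw counts and the planned raw tests alongside, including those at each assessment point.
- Keep the raw tests alone for SUD admissions and for other adverse events with too few events or no prior-year counterpart.

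The cost is SAP wording, one earlier 12-month extraction window from the same datasets and slightly more modelling. No new patient contact is needed.

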8. PROJECT MANAGEMENT

8.1 Project Management Overview

The overall study structure includes a central study coordinating center located at the Minneapolis VA and ten VA sites where patients will be enrolled and receive the interventions. The coordinating center will manage core research activities including centralized recruitment and outcome assessment; engagement activities; data management, programming, and statistical analysis; data and safety monitoring; and regulatory compliance. Local sites will enroll patients and implement the interventions. Local site study personnel include local site investigators and at least one local site study coordinator. Local study coordinator absences or vacancies may be covered by other local approved study staff or coordinating center staff if needed. Intervention clinicians are VA employee volunteers who are being trained and evaluated; those who are not co-investigators will be considered research participants themselves.

8.2 Study Application

The coordinating center data team will create a customized web-based front end application to support research tasks. The “front end” is a secure web page on the VA intranet, but the actual data “back end” is stored on a secure VA server maintained and regularly backed up by Region 2 of VA Office of Information Technology. Only approved specific study personnel are granted access to this application.

A user manual will be created as a guide for all study personnel. Contact information for patients selected for participation will be stored in the database. Additional tables will be created for scheduling and tracking study contacts. Coordinating center data team personnel will control access to the study application and provide access to research personnel at the coordinating center and local sites according to their research scope of practice. Study personnel will use the application to complete tasks including preparing recruitment mailings, conducting standardized eligibility screening, scheduling participant contacts, randomizing participants, and recording completed outcome assessments and adverse events.

8.3 Local Site Facilitation

During the start-up phase at each site, the study leadership team will support establishment of intervention clinical teams using an implementation facilitation approach. This will include the following activities:

- Assignment of each local site to a designated facilitator (Drs. [name], [name], and [name]) for ongoing interactive problem-solving and support
- Development of detailed local site implementation plans
- Conduct of pre-implementation local site visits to accomplish the following objectives:
 - Describe rationale for the study and evidence for the interventions through research presentations and local stakeholder briefings
 - Develop relationships with local stakeholders and clinicians
 - Identify local site implementation challenges and opportunities
 - Refine local site implementation plans, including timetable
- Establishment of cross-site collaborative groups to support local site clinical champions and clinician intervention teams

8.4 Local Site Rollout

Enrollment at individual local sites will be initiated on a rolling basis once sites have met all criteria for enrollment launch. We plan to initiate enrollment at 1-3 sites per month over 3-5 months, with the order of launch depending on local site readiness.

The PM will coordinate training for study coordinators and research assistants at all sites. The Minneapolis coordinating center team will use audio-visual resources to conduct “mock” consent sessions and share them with sites as a training tool. Ongoing training will be provided throughout the study as new personnel come onboard or if questions or issues arise at local sites.

Prior to beginning enrollment at each site, the PI and overall study project manager (PM) will meet with the local site PIs and coordinators to ensure they fully understand informed consent, randomization, and data management procedures. A local site start-up checklist of required approvals and trainings will also be completed. Prior to initiating enrollment at any local site, all of the following criteria must be met:

- Approvals obtained from the VA Central IRB (i.e., the Local Site Investigator application), the Research & Development committee of record, and any additional regulatory bodies as required at the local site (e.g., University IRB)
- Site study coordinator and investigator(s) trained in study research protocols, including informed consent, randomization, adverse events reporting and other data/safety monitoring procedures
- Intervention clinician teams established and trained in clinical background, intervention protocols, documentation templates, educational materials, study resources, and local site protocols for clinical coverage

8.5 Cross-Site Communication

Current protocol, informed consent, and study intervention documents will be maintained on the study SharePoint site. All amendments and modifications to the protocol, the informed consent form, and the HIPAA authorization will be promptly communicated to local sites by email. Regular cross-site study meetings will include discussion of any anticipated or recent changes to the study protocol and procedures.

8.6 Local Site Contingency Plans

In case of significant delays in meeting enrollment launch criteria, despite facilitation efforts, site discontinuation and replacement will be considered. Consideration of site discontinuation or replacement will be discussed with engagement partners and PCORI staff prior to making a decision. If a decision is made to change a site, prior approval will be requested from PCORI as outlined in the contract for the funded research project.

9. IMPLEMENTATION PROCESS EVALUATION

9.1 Process Evaluation Overview

Goals of the implementation process evaluation are threefold: 1) to increase the relevance of the primary research findings to patients, clinicians, and health care decision-makers; 2) to increase the likelihood of timely translation of research findings into diverse practice settings; and 3) to generate information to guide interpretation of primary trial findings. In addition to scientific reports and manuscripts, products of this process evaluation will include an implementation toolkit (developed in collaboration with study partners) to support implementation of successful study interventions in diverse practice settings.

9.2 Process Evaluation Questions

The RE-AIM and PARIHS frameworks related to dissemination/implementation were used to facilitate identification of questions related to the context of study sites and the process of implementing the interventions. Implementation process evaluation questions include the following:

- What was the level of organizational readiness relative to the clinical interventions, including staff's related perceptions/attitudes?
- What barriers or facilitators to the successful implementation of the study protocol were found (e.g., to what extent were clinic staff and leadership perceived as visibly supportive)?
- How were the interventions received by patients (e.g., how many of the selected patients actually participated in the interventions and were they different from those who did not)?
- How were the interventions received by patients who did participate actively (e.g., in terms of completion vs. drop-out rates and perceptions of usefulness to their treatment)?
- Were the study interventions provided with high fidelity?
- What, if any, recommendations do patients or clinicians have for changes to the interventions that they feel would improve the "fit" or effectiveness of the interventions?
- To what extent did facilities plan to sustain the interventions following completion of the study? If they planned to sustain an intervention, what barriers did they anticipate? How did they plan to modify the intervention from the original study protocol to address those barriers? If they did not plan to sustain an intervention, what considerations or barriers led to that decision?

9.3 Process Evaluation Methods

Qualitative or basic quantitative data will be collected as appropriate to each question. Approaches include the following:

- Evaluation team observations: Each study site will have an assigned member of the implementation evaluation team to take observational notes of interactions as described in Section 6.4.2.
- Information on patient recruitment and completion rates: Recruitment rates will provide an estimate of how appealing the interventions are to the targeted patients. Patients who decline study participation in the intervention will be asked their reason for declining. Intervention completion vs. drop-out rate will also provide information on acceptability of the interventions. Demographic and clinical data will be examined for the purpose of comparisons of decliners to enrollees and intervention completers to drop outs.
- Fidelity monitoring: In the event of negative findings (no intervention effect) for an intervention arm, it is essential to rule out implementation failure as a cause. Fidelity will be assessed as described in Section 5.8.
- Patient semi-structured interviews: A subset of participants enrolled in each study intervention will be interviewed at the end of their intervention participation as described in Section 6.4.1.
- Semi-structured interviews with clinician participants and other VA employees: A sample of clinicians directly involved in the interventions and other VA clinical and administrative staff at enrolling sites will be interviewed at the end of the intervention period as described in Section 6.4.1.

9.4 Qualitative Analysis

Qualitative data from the evaluation team observational notes and the transcribed semi-structured interviews will be analyzed by intervention evaluation team members, who are all experienced with qualitative data coding and analysis. They will review the transcripts and develop an initial coding list. They will each code an initial set of documents using the initial coding list, adding codes as new insights emerge. Consensus coding meetings will be held for review of consistency in coding. Inconsistencies will be resolved through mutual discussion. When evaluation team members have reached consistency in coding, remaining documents will be coded by one team member with 20% cross-coded by a second team member. Transcripts and codes will be entered into a software package designed to handle unstructured qualitative data (NVivo) to facilitate identification of themes and supporting quotations. Inductively derived themes will be compared with the elements identified by the PARIHS successful implementation model and RE-AIM dissemination model to further facilitate analysis and interpretation. All process data will then be triangulated, where appropriate, and used to answer the targeted questions and facilitate interpretation of summative findings.

